3.1 Target Population

We will recruit 100 women, aged 35 to 58 years old, who have undergone a RRSO within the previous 15 years and are currently reporting impairment in some aspect of their daily function. We anticipate a drop-out rate of 10%. Given that the composition of the proposed study population will reflect the Greater Philadelphia referral base, we will make attempts to enhance the recruitment of minorities, but we are limited by the racial and ethnic make-up of women who typically seek oophorectomy for prevention of breast and ovarian cancer.

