4.1 Statistical Analysis

Summaries of each outcome (BADDs scores, performance on the cognitive tasks, Glut, and BOLD signal) under each treatment condition (baseline, LDX, and placebo) will be examined using histograms, boxplots, and normal probability plots. Transformations of the outcomes will be considered as necessary to meet modeling assumptions. General linear regression (mixed models) will be employed to estimate the association between each outcome, treatment condition and cross-over sequence while accounting for the nonzero correlation among the repeated observations within individuals.

Aim 1: Total BADDs score at each time point will be examined for an interaction effect between time (pre vs. post) and treatment (LDX vs. placebo) to assess whether within-subject total BADDs score is significantly reduced post LDX treatment rather than post placebo. Baseline BADDs scores will be dichotomized at the median score and considered as a covariate in the mixed effects models. Additional interaction terms for baseline group by time (pre vs. post) and baseline group by treatment (LDX vs. placebo) will be added to the model to test whether treatment effects differentially affect those with higher baseline scores.

Aim 2: Similar models will evaluate BADDs subscores, cognitive task performance, and L-DLPFC Glut levels. Similar mixed models will assess associations between change in specific BADDs domains with identified deficits in executive function and change in DLPFC Glut levels.

Aim 3: We will quantify associations between baseline percentage BOLD signal change during performance of the n-back (3-back) and L-DLPFC Glut.

Current methods for fMRI analyses are as follows: Functional scans will be realigned, normalized, time-corrected, and spatially smoothed by an 8 mm FWHW Gaussian kernel. The time series will be high-pass filtered to correct for drift across the scan. For blocked designed experiments (3-back), regressors will represent trial conditions; for the event-related design

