4.2 Rationale for sample size

Sample size is estimated for the 3 primary outcome measures: BADDS scores, DLPFC Glut levels, BOLD signal activation during the N-Back Task.

Assuming a type I, alpha, error of 5%, and 80% power, we anticipate being able to detect a 0.3 SD difference between within subject change under active LDX and placebo conditions with 88 participants. Based on our pilot data for total BADDS score, we will have 80% power to detect as small as an 8.4% difference in BADDS total score when comparing placebo to LDX administration. Given our pilot data from naturally menopausal women, this effect size corresponds to a 19% difference between active LSX and placebo in organization and activation for work, and 15% for attention/concentration BADDS subscales. We are conservatively powered for an effect size of 0.3 SD, meaning that we have sufficient power to examine a number of different covariates and possible predictors of outcome in this study.

Given our pilot data for levels of Glut in the left DLPFC, we will have 80% power to detect as small as a 2.6% reduction in Glut for active LDX administration compared to placebo. A similar 0.3 SD can be detected for BOLD signal in left DLPFC. This corresponds to a 25% difference in BOLD signal change between placebo and LDX for 3-back task.

5 Safety and Adverse Events

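### Aim 1 tests whether the LDX effect depends on baseline severity using a median split, which costs roughly a third of the information if the dependence is linear, and omits the interaction term the question needs

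*Combined protocol and SAP*

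**What the plan says.** Section 4.1 (Aim 1) analyses total BADDs at each time point for an "interaction effect between time (pre vs. post) and treatment (LDX vs. placebo"). It then says: "Baseline BADDs scores will be dichotomized at the median score and considered as a covariate in the mixed effects models". Next, "Additional interaction terms for baseline group by time (pre vs. post) and baseline group by treatment (LDX vs. placebo) will be added to the model", and the stated purpose is "to test whether treatment effects differentially affect those with higher baseline scores". So the split is the planned inferential test of effect modification and not just a display device.

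No external cut-point is given, so the natural reading is the median of the women enrolled. The documents give no continuous-baseline analysis, no sensitivity analysis and no reason for the split. They also do not say which baseline is meant. A BADDs score is needed at screening for eligibility (section 3.3), and section 2.1 has a separate baseline visit in each of Trials A and B.

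Section 4.2 sizes the trial for the overall comparison only, a "0.3 SD difference between within subject change under active LDX and placebo conditions with 88 participants". It then says this leaves "sufficient power to examine a number of different covariates and possible predictors of outcome", without a calculation for any interaction.

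**The concern.** Total BADDs is the sum of a 40-item scale, and the plan analyses it as a number when it is the outcome. When it is the baseline, the plan cuts it in two. Women just either side of the median are then treated as different, and women far apart on the same side as identical. Baseline severity is the only moderator of the LDX effect named in section 4.1, so the loss falls on the one question of this kind that the plan asks. Aim 2 uses similar models for the subscores, cognitive tasks and glutamate, so the split may carry over to them.

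The second problem is in the model terms. If the treatment effect is time by treatment, a treatment effect that depends on severity is a three-way interaction, and none is listed. The severity question could then be answered wrongly or diluted, however baseline is coded.

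**Working it through.** **The plan's own figure.** Inputs from section 4.2: alpha 5%, power 80%, effect 0.3 SD of the within-subject difference. Sidedness is not stated. Two-sided, normal approximation: n = ((1.960 + 0.842)/0.3)² = 87.2, rounded up to 88. This reproduces the stated 88. With the 10% dropout of section 3.1, 88/0.90 = 98, in line with "We will recruit 100 women, aged 35 to 58 years old". This calculation does not involve baseline severity.

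**Information kept by a median split.** Assume the LDX effect changes linearly with baseline score X. The relative efficiency of the high/low indicator is its squared correlation with X. For a normal X this is 2/π = 0.637, a loss of 36%.
- 0.637 × 88 = 56: after the split, 88 women carry the information of about 56.
- 88/0.637 = 138: about 138 women would be needed to break even.

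**Sensitivity to shape.** The documents give only an entry floor of 20 (section 3.3), so the shape is an assumption. Results by simulation:

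| Assumed baseline shape | Loss | Equivalent of 88 women |
|---|---|---|
| Uniform | 25% | 66 |
| Normal truncated at 20 (mean/SD before truncation 40/15, 35/15, 30/15, 50/20, 20/20) | 34% to 38% | 54 to 58 |
| Normal | 36% | 56 |
| Gamma, shape 4 | 41% | 52 |
| Gamma, shape 2 | 45% | 49 |
| Exponential | 52% | 42 |

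**Hypothetical power example (normal baseline).** The plan gives no modifier effect size, so take the correlation that 88 women detect with 80% power.
- Continuous: r = tanh(2.802/√85) = 0.295.
- After the split: r × √(2/π) = 0.295 × 0.798 = 0.235. Power = Φ(atanh(0.235) × √85 − 1.960) = 59.9%.
- 20,000 simulated trials gave 79.5% against 59.8%.

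On the slope scale, the smallest effect detectable with 80% power at n = 88 is 2.802/√88 = 0.30 SD per baseline SD with the continuous score. With the split it is 0.30/0.798 = 0.37. Between the two halves, the smallest detectable difference in LDX effect is 2 × 2.802/√88 = 0.60 SD, twice the 0.3 SD in section 4.2.

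**Can the listed terms carry the question?** Take a noise-free example with arbitrary values: the LDX effect (time by treatment) is −5 in the low group and −11 in the high group. Fit group, time, treatment, time × treatment, group × time and group × treatment.
- The fitted time × treatment effect is −8 for both groups.
- Group × time and group × treatment each come out at −3.
- Every one of the eight cell means is missed by 0.75.

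The true difference of 6 between groups cannot be represented. Half of it leaks into each two-way term, where it is mixed with anything else those terms absorb.

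**The case against.** The strongest reply is about scope: the LDX versus placebo comparison is within-subject, so a baseline split does not weaken it. That is right. A reader might infer that the trial's own power falls from 80% to 60%, or that 88 is too few. The documents support neither. The 0.295 was solved back from 88 women and 80% power, and it is not a figure in the plan.

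Second, the size of the loss rests on linearity and on an unknown baseline shape, so a flat statement that a third of the information is lost would go too far. That stands, and it is why the range is given.

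Third, the split is not without merit. It is fixed in advance, gives equal groups and prevents an outcome-driven choice of cut-point. If the true effect were a step exactly at the median, it would be the better analysis: for a 0.6 SD step at n = 88, simulated power is 79% with the split and 59% with the continuous score. But nothing in the documents points to such a step. Nor would it be right to say that a split result cannot be carried to another cohort, since the observed median can be reported on the BADDs scale. It is only less convenient.

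Fourth, one could argue that the three-way term is implied by the stated purpose, or that group × treatment would suffice if only end-of-trial scores were modelled. But Aim 1 models the score at each time point and lists group × time, so pre-treatment scores are in the model, and the needed term should be written down.

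**Conclusion.** The point holds for the severity question only. With a roughly linear modifier effect, the median split loses about 36% of the information for a normal baseline, 34% to 38% for the normals truncated at 20 that were tried, and about 25% to 52% across all shapes examined. The text itself is clear; the size is conditional on those assumptions. Independently of any distribution, the listed interactions do not test whether the Aim 1 treatment effect varies with severity, because group × time × treatment is missing. The primary comparison and N = 88 stand. The section 4.2 remark about power for predictors has no interaction calculation behind it, but that gap is separate from the median split and would remain with a continuous score. This is a worthwhile improvement to a supplementary analysis and does not threaten the main result.

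**What to change.** Replace the two sentences on baseline BADDs in section 4.1 with wording such as:

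*Differential LDX effect by severity will be tested with Trial A pre-treatment total BADDs as a centred continuous score, by regressing each woman's LDX-minus-placebo difference in end-of-trial BADDs on that score, with sequence in the model. A quadratic or spline term will check linearity. Median groups will be used for display only.*

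A mixed model with a continuous baseline × time × treatment term is the alternative. It handles the pre-treatment scores differently: if these stay in as outcome rows, the covariate equals the outcome in the Trial A pre-treatment row. The plan should therefore name one route in advance. It should also say whether the same approach applies to the Aim 2 outcomes.

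The cost is a few sentences before analysis begins, with no new data, visits or participants. The downsides are that the test assumes approximate linearity, that it would be less efficient if the true effect were a step at the median, and that the difference regression uses only women with both end-of-trial scores.

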End of Trial Scan: After the 6-week period, subjects will be scheduled to undergo their end of Trial A ¹H-MRS and fMRI scan session, which will take approximately 75 minutes. Subjects will be instructed to present to the Penn Center for Women's Behavioral Wellness approximately 2.5 hours before their scheduled scan to complete cognitive testing and behavioral assessments

regarding their mood and emotions. Subjects will then be escorted to the CMROI by the study CRC where they will be scanned and asked to perform a series of tasks assessing their memory and attention. In total, the end of Trial A scan will require approximately 4 hours to complete. The completion of this visit concludes all visits for Trial A. Upon completion of the visit and Trial A, subjects will be given the study drug for the entirety of Trial B (either placebo or LDX) and instructed to begin taking the medication after the washout period, as directed by the study provider.

Following an approximate 2-week washout period, subjects will complete their Trial B Baseline Visit, initiating the start of Trial B and medication usage. With the exception of the first baseline scan and cognitive testing, subjects will undergo the same study procedures for Trial B as they did for Trial A. Subsequent to their last scan, subjects will be required to bring their scales, blood pressure cuffs and unused capsules/empty bottles back to the study team so that they can be returned to Penn Investigational Drug Service (IDS).

The primary investigator and research staff will unblind themselves to the drug treatment that was administered in each trial upon each participant's completion or discharge from the study.

Remote End of Trial Visit: After the 6-week period, subjects will be scheduled to undergo their end of trial visit which will require approximately two hours. On the day of the remote end of trial visit, subjects will meet remotely with a member of the study team to complete behavioral assessments regarding their mood and emotions and complete cognitive testing. The completion of this visit concludes all visits for Trial A. Upon completion of the visit and Trial A, subjects will return the prescription bottle and any remaining study drug from Trial A so that they can be returned to Penn Investigational Drug Service (IDS). At this point, all subjects will be instructed to complete an approximate 2-week wash out period before continuing to Trial B.

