3.3 Key inclusion criteria

1. Females aged 35 to 58 years;
2. Have undergone risk-reducing bilateral salpingo-oophorectomy (RRSO) within the previous 15 years AND were premenopausal at the time of RRSO;
3. Score of ≥ 20 on the Brown Attention Deficit Disorder Scale (BADDs);
4. Onset of executive function difficulties occurred post RRSO;

5. Clean urine drug screen (nicotine and marijuana are permissible). Potential false positive screenings will be reviewed and exclusionary based on PI discretion;
6. Are fluent in written and spoken English;
7. Are able to give written informed consent (obtained at screening visit);
8. Have a high school diploma or equivalent degree (i.e., GED), as per subject report;
9. *If using aromatase inhibitors or tamoxifen:* Must have been on a stable dose for at least 6 months;
10. *If completing visits remotely:* Must have access to a telecommunications application (i.e., Skype), email, scanner/fax machine, and a private area that enables the protection of participant confidentiality.

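### Aim 1's test of whether the LDX effect varies with baseline BADDs omits the baseline × time × treatment term, and the claimed power for predictors has no support

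*Combined protocol and SAP*

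**What the plan says.** In section 4.1, Aim 1 examines total BADDs for an "interaction effect between time (pre vs. post) and treatment (LDX vs. placebo"). It continues: "Baseline BADDs scores will be dichotomized at the median score and considered as a covariate in the mixed effects models". It then states that "Additional interaction terms for baseline group by time (pre vs. post) and baseline group by treatment (LDX vs. placebo) will be added to the model", and gives the purpose as "to test whether treatment effects differentially affect those with higher baseline scores". No baseline × time × treatment term appears anywhere in the plan.

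The opening paragraph of 4.1 describes outcomes "under each treatment condition (baseline, LDX, and placebo"), a three-level coding. Aim 1 instead names time and treatment as two separate two-level factors.

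The baseline score is not defined, and there are three candidates:
- the eligibility score in section 3.3 ("Score of ≥ 20 on the Brown Attention Deficit Disorder Scale (BADDs"));
- the Trial A pre-treatment score;
- the Trial B pre-treatment score, since section 2.1 says "subjects will complete their Trial B Baseline Visit, initiating the start of Trial B and medication usage".

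Section 4.2 gives 80% power at 5% alpha for a "0.3 SD difference between within subject change under active LDX and placebo conditions with 88 participants". It infers from this that power is also enough to study several covariates and predictors of outcome. No calculation for an interaction or subgroup is shown.

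**The concern.** The two terms listed do not match the question they are meant to answer. Group × time averages the pre-to-post change over LDX and placebo periods, so a placebo or time response that differs by severity moves it as much as a differential LDX response does. If women are split on a score that is also an outcome value in the model, regression to the mean moves it with no drug effect at all. Group × treatment, coded LDX versus placebo over both pre and post rows, dilutes the effect because the pre rows carry none.

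Three wrong readings could follow. A significant group × time term could be reported as greater LDX benefit in more impaired women. A real moderator effect could be reported at half its size. Null predictor analyses could be taken as adequately powered. Aim 2 uses similar models for the BADDs subscores, cognitive tasks and Glut, so the specification may be repeated there.

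**Working it through.** **1. The plan's own figure.** Inputs from 4.2: alpha 5%, power 80%, effect 0.3 SD, N = 88. With a two-sided paired comparison, n = ((1.960 + 0.842)/0.3)² = 87.2, rounded up to 88. A one-sided test would give 69, so two-sided is assumed. By paired t-test, power at 88 is 79.5%. The 88 therefore reproduces for the overall contrast, with the 0.3 SD in units of the SD of each woman's difference in change, D = (LDX post − pre) − (placebo post − pre). Nothing is left over.

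**2. What each term estimates.** Let the LDX effect be larger by δ in the high-baseline group. Apart from a constant, the high-minus-low differences in mean are 0 (LDX pre), δ (LDX post), 0 (placebo pre) and 0 (placebo post).
- Group × time × treatment: (δ − 0) − (0 − 0) = δ.
- Group × treatment, no three-way term: (0 + δ)/2 − (0 + 0)/2 = δ/2.
- Group × time, no three-way term: (δ + 0)/2 − (0 + 0)/2 = δ/2.

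If the groups instead differ by γ in a response common to LDX and placebo, group × time equals γ and the other two are 0.

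This was checked by simulation: 3,000 crossovers per setting, 88 women, 44 per sequence, unit-variance scores, equal visit correlation ρ, no carry-over. For a true difference of −0.50 outcome SD at ρ = 0.5, 0.7 and 0.9:
- group × treatment averaged −0.256, −0.252 and −0.252;
- the three-way term averaged −0.500, −0.497 and −0.496;
- the LDX-versus-placebo contrast under three-level coding averaged −0.506, −0.500 and −0.501.

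Power is equal because the group × treatment contrast has SD √(1−ρ) against 2√(1−ρ) for D: half the effect over half the standard error. Simulated power was 39% against 38% at ρ = 0.5, and 57% for both at ρ = 0.7.

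**3. Regression to the mean in group × time.** Assume no LDX effect and a median split on the Trial A pre score. For a normal score the two halves differ by 2 × 0.798 = 1.596 SD at that visit and by 1.596ρ at the other three. Group × time then has expectation 1.596ρ − (1.596 + 1.596ρ)/2 = −0.798(1−ρ). Its standard error is √(1−ρ) × √(2/44) = 0.213√(1−ρ).

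| ρ | Shift (SD) | SE | Shift/SE | Rejection, formula | Simulated, Trial A split | Simulated, separate screening split |
|---|---|---|---|---|---|---|
| 0.5 | 0.399 | 0.151 | 2.65 | 75% | 75.0% | 5.5% |
| 0.6 | 0.319 | 0.135 | 2.37 | 66% | 66.1% | 5.4% |
| 0.7 | 0.239 | 0.117 | 2.05 | 54% | 53.0% | 5.0% |
| 0.8 | 0.160 | 0.095 | 1.67 | 39% | 39.3% | 4.7% |
| 0.9 | 0.080 | 0.067 | 1.18 | 22% | 21.5% | 4.6% |

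In the same null runs with the Trial A split, group × treatment was rejected in 3.8% to 5.0%.

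**4. Power for predictors.** A median split of 88 gives 44 against 44. In SD of D, by two-sample t-test:
- power at 0.3 SD is 28.5%;
- 80% power is reached at 0.604 SD;
- 80% power at 0.3 SD needs 176 per group, or 352 women (350 by the normal approximation).

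The SD of D is 2√(1−ρ) = 1.41, 1.10 or 0.63 outcome SD at ρ = 0.5, 0.7 or 0.9, so 0.604 SD of D is 0.85, 0.66 or 0.38 outcome SD.

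For a continuous baseline, Fisher's z gives (1.960 + 0.842)/√(88 − 3) = 0.304, which is a correlation of 0.295 with D.

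**The case against.** The missing term costs little under the simple assumptions. The plan promises a test, not an estimate, and group × treatment tests the right hypothesis with the same power as the three-way term. That stands under equal visit correlations. But the plan states no covariance structure. Under other structures tried, group × treatment recovered between 0.29 and 0.67 of the true difference, and a period random effect cut its power from 80% to 50% at 0.6 SD of D. So the attenuation is general, while exactly one half, and equal power, are not.

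The three-level condition in the opening paragraph of 4.1 can be read into the model sentence that follows it, and would give the full effect. That makes the text ambiguous. It does not clear it, because Aim 1 spells out two-level coding both for the main effect and for the added terms.

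The high false-positive rate needs the split to be on the Trial A score. That is correct, and the documents do not settle the choice. The reassurance from a separate screening score is conditional too: with correlations that decay over time, a screening split gave 69% to 82% rejection of group × time, and 7% to 8% for group × treatment.

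The 4.2 sentence covers covariates and main-effect predictors as well as moderators, and claims no power for a 0.3 SD interaction. That is fair. The inference is unsupported; an interaction larger than about 0.6 SD of D would not be expected to be missed.

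**Conclusion.** The concern holds. The plan names two interactions as tests of differential LDX response. One is not such a test, and the other understates the difference: by half with balanced data, equal variances and equal visit correlations. With the baseline undefined, the null rejection rate of group × time for 88 women ranges from about 5% (separate screening score, equal correlations) to 75% (Trial A score, ρ = 0.5). The value of ρ is an assumption, since the documents give none.

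The claim of adequate power for predictors does not follow from a sample size that only just reaches 80% for the overall 0.3 SD contrast. A two-group split needs about twice that difference. These power figures assume that D has the same SD in both halves.

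The primary time × treatment test and the 88 are not affected. This should be corrected before analysis because it changes what may be concluded about who benefits.

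**What to change.** - State which BADDs score is the baseline, and enter it as a continuous covariate. A median-split table can stay as description.
- Test moderation by baseline × treatment in a model of post-treatment scores, or by baseline × time × treatment if pre-treatment scores remain as outcomes. Apply the same rule to the Aim 2 models.
- State that baseline × time is not interpreted as differential response to LDX. It may remain as a lower-order term.
- Replace the predictor-power sentence in 4.2 with:

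> For a two-group split of 88 women, 80% power requires a between-group difference in effect of about 0.6 SD of the within-woman LDX-minus-placebo difference in change; for a continuous baseline score it requires a correlation of about 0.29 with that difference. Predictor analyses are exploratory.

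The cost is SAP wording and one less favourable power statement. Sample size, visits and the primary test do not change.

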Our group has explored the use of other pharmacologic strategies to target executive systems with the goal of improving symptoms of executive function difficulties. We have conducted two RCTs with medication marketed for the treatment of attention deficit hyperactivity disorder (ADHD), one with the non-psycho stimulant atomoxetine (ATX, Straterra®) and two with the pro-drug and psycho stimulant lisdexamfetamine (LDX, Vyvanse®) in the treatment of executive function difficulties in perimenopausal and menopausal women. Women who participated in the ATX study reported a significant improvement in concentration/attention and working memory domains of the Brown Attention Deficit Disorder Scale (BADDs) ([name] et al., 2011). Participants in both LDX studies were also invited to undergo the brain-imaging paradigm that is described for the current study.

[figure not shown]
Figure 1 shows the main outcome of the published results, specifically that LDX was more effective than placebo at decreasing scores in 4 of the 5 BADDs subscales ([name] et al., 2015). Findings from the imaging sub-study indicated that baseline glutamate (Glut) levels were correlated with baseline severity of total BADDs scores, meaning that individuals presenting at baseline with higher severity of executive function difficulties also had higher Glut levels within the left dorsolateral prefrontal cortex (DLPFC) at baseline. Additionally, the decline in BADDs subscale 1 (Organization and Activation) scores during LDX vs. placebo treatment was negatively associated with increase in left DLPFC blood oxygen dependent (BOLD) signal during a working memory task (N-Back). That is, the increase in left DLPFC BOLD signal to active drug compared to placebo was greater in people who had greater improvement in BADDs score on LDX vs. placebo. These findings provide important evidence of co-occurring behavioral and brain changes with LDX treatment. Applying this paradigm in a larger sample of women from whom we will also acquire neurocognitive data to assess objective changes in function will provide important information regarding the mechanism of therapeutic action of LDX in this unique population.

1 Study Objectives

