5.3 Risk/Benefit Assessment

This study represents more than minimal risk to the subject, as individuals will undergo neuroimaging and treatment with LDX, which they may never have otherwise taken. Should this study show that LDX administration improves executive function outcomes of interest and is correlated with changes in left DLPFC glut concentrations and BOLD signal, we will have additional evidence that psychostimulant –related changes in brain neurochemistry and neuronal function are clinically relevant.

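### Aim 2 does not isolate the LDX-specific link between Glut change and BADDs change, although the drug-mechanism inference depends on it

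*Combined protocol and SAP*

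**What the plan says.** Section 4.1 describes mixed models with treatment condition and cross-over sequence that allow for repeated observations on each woman. Aim 1 tests a time-by-treatment interaction. Aim 2 applies like models to the other outcomes and adds: "Similar mixed models will assess associations between change in specific BADDs domains with identified deficits in executive function and change in DLPFC Glut levels". It gives no LDX-minus-placebo contrast, no treatment-by-Glut-change term and no separation of within-woman from between-woman association.

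Glut has one pre-treatment measurement. Section 2.1 states: "With the exception of the first baseline scan and cognitive testing, subjects will undergo the same study procedures for Trial B". The payment table in 2.5 lists the Trial B baseline as having no scan, and 4.1 lists a single baseline condition beside LDX and placebo.

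The intended inference is about the drug. The opening summary presents LDX-induced change in prefrontal glutamate as a possible therapeutic mechanism. Section 5.3 says that if LDX improves outcomes and this goes with changes in Glut and BOLD, "we will have additional evidence that psychostimulant –related changes in brain neurochemistry and neuronal function are clinically relevant".

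The Background reports two pilot results. Before treatment, "baseline glutamate (Glut) levels were correlated with baseline severity of total BADDs scores". For BOLD the contrast was LDX against placebo on both sides: "the increase in left DLPFC BOLD signal to active drug compared to placebo was greater in people who had greater improvement in BADDs score".

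**The concern.** The scientific question is whether women whose Glut moves more because of LDX also improve more because of LDX. In a crossover, each woman's LDX-minus-placebo difference answers that. One slope fitted to two change records per woman answers a broader question: whether changes from any source go together. Part of that slope comes from comparing women on their average change over both conditions, which contains the common baseline scan and any response to placebo or time.

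Aim 2 is the only planned analysis that ties Glut change to symptom change; Aim 3 and the fMRI/MRS analysis relate BOLD to Glut. If its slope is significant because of the between-woman part, a non-drug association could be reported as the mechanism of LDX.

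**Working it through.** **The plan's own figure.** Section 4.2 gives "Assuming a type I, alpha, error of 5%, and 80% power" and a "0.3 SD difference between within subject change under active LDX and placebo conditions with 88 participants". The paired normal approximation, two-sided, gives n = ((1.960 + 0.842)/0.3)² = 87.2, so 88. With the 10% drop-out of section 3.1, 88/0.9 = 97.8, so 98, within the 100 to be recruited. The figure reproduces. It concerns mean differences, not the Glut-BADDs association, and some participants will have no imaging (2.1 and 3.7), so 88 is an upper case here.

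**Algebra.** Let G0, GL and GP be Glut at baseline, end of LDX and end of placebo. The two changes are GL − G0 and GP − G0.
- Within-woman part: (GL − G0) − (GP − G0) = GL − GP. The baseline cancels.
- Between-woman part: (GL + GP)/2 − G0. The baseline stays, with any non-drug change common to both conditions.

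A single random-intercept slope is a weighted blend of the two. A treatment term removes mean shifts but does not separate them.

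**Assumptions (not in the documents).** For each measure: stable-trait variance 0.5, visit variance 0.5, non-specific change variance 0.15, individual LDX-response variance 0.15. LDX responses in Glut and BADDs are independent except in the true-link row.

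The trait cancels in change scores. The woman-mean change has variance 0.5/2 + 0.5 + 0.15 + 0.15/4 = 0.9375, and the LDX-minus-placebo difference has 2 × 0.5 + 0.15 = 1.15. Implied correlations:
- Baseline-visit covariation that gives an observed baseline r of 0.2 (covariance 0.2): 0.2/0.9375 = 0.21 between woman-mean changes, 0 between differences.
- Non-specific changes correlated 0.5: 0.5 × 0.15/0.9375 = 0.08 between woman-mean changes, 0 between differences.
- Visit-level correlation 0.3 at every visit: 2 × 0.5 × 0.3/1.15 = 0.26 between differences, so the difference analysis is not immune.
- True LDX-response link of 0.7: 0.7 × 0.15/1.15 = 0.09 between differences.

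**Simulated rejection at two-sided 5%** (2,000 runs per case; Monte Carlo standard error near 5% is √(0.05 × 0.95/2000) = 0.5 points). The single slope has treatment and period in the model; the difference regression adjusts for sequence.

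| Case | Single slope, N = 88 | Difference, N = 88 | Single slope, N = 60 (assumed imaging N) |
|---|---|---|---|
| Shared Glut baseline only | 4.8% | 4.8% | 5.6% |
| Stable-trait correlation, baseline r 0.3 | 5.5% | 5.0% | 5.9% |
| Non-specific change r 0.5 | 9.6% | 6.0% | 9.6% |
| Baseline-visit-only, r 0.1 / 0.2 / 0.3 | 9.4 / 31.2 / 60.6% | 4.6 / 5.4 / 5.8% | 9.6 / 23.4 / 46.7% |
| Same, BADDs with own Trial B baseline, r 0.2 / 0.3 | 19.3 / 31.6% | 4.7 / 5.1% | 14.2 / 26.0% |
| Visit-level r 0.3 at every visit | 91.2% | 67.0% | 78.4% |
| True LDX-response link 0.7 | 13.6% | 13.4% | 10.6% |

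Under a second set of assumptions (visit SD 1, one shared baseline for both measures), non-specific change correlated 0.3 and 0.5 gave 13% and 29% for the single slope and about 5% for the difference. Across the variance assumptions tried, this route gives roughly 7% to 30%.

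**The case against.** Four points on the other side have force.

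- Pooling is inferred. The sentence names no contrast, and models like Aim 1's could be given a treatment-by-Glut-change term. The pilot shows that the group knows the LDX-versus-placebo contrast. This stands: the supportable statement is that the text does not isolate the LDX-specific part, not that the wrong model has been chosen.
- A reader might infer from the pilot's baseline correlation that false-positive rates of 30% to 60% are to be expected. The documents do not support that. A stable-trait correlation cancels in change scores. Covariation at every visit troubles the difference analysis too. Only covariation confined to the baseline visit gives the high rates, and nothing favours that reading. The Trial B baseline visit also appears to repeat the behavioural ratings, so BADDs may have its own second baseline, which lowers these rates.
- A reader might also infer that mean LDX effects on both measures alone create an association. That requires a model with no treatment term (12% and 40% in two simulated cases, against about 6% with the term). Section 4.1 names treatment condition among the model terms, so this is a strained reading.
- Section 5.3 is a risk/benefit paragraph, not a decision rule. It is conditional on clinical improvement, also involves BOLD, and claims only additional evidence. That limits the stakes, but the inference it describes is still drug-specific.

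**Conclusion.** The concern holds in a limited form. Aim 2 does not separate the association due to LDX from association due to anything else, while the summary and 5.3 draw a conclusion about LDX. One shared Glut baseline is not in itself a fault: with it alone, or with a stable-trait correlation, error stays at about 5% to 6%. Inflation needs non-specific changes that covary (roughly 7% to 30% at correlations of 0.3 to 0.5) or covariation at the baseline occasion. The baseline route gives lower rates if BADDs has its own Trial B baseline, and generally lower rates at a smaller imaging N. Every rate rests on assumed variances and correlations and is illustrative. The difference regression stayed near its nominal level in every no-link case without same-visit covariation. The point concerns a secondary, mechanistic analysis; the primary comparison of total BADDs is untouched. It is a cheap improvement.

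**What to change.** In 4.1, Aim 2, specify the test as a regression across women of the end-of-LDX minus end-of-placebo difference in each BADDs domain on the end-of-LDX minus end-of-placebo difference in left DLPFC Glut, with an intercept and sequence. Equivalently, use a mixed model of the end-of-trial values with treatment and period, split Glut into the woman's mean and her deviation from it, and test only the deviation. Report the between-woman slope as descriptive. In 5.3, rest any statement about drug mechanism on the within-woman association.

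This needs wording and no new data. It has three costs:
- Women who miss one end-of-trial scan drop out of this secondary analysis.
- Power may fall slightly. In three simulated cases with larger individual LDX responses it went from 35% to 34%, stayed at 71%, and went from 85% to 81%. It may be low in any case: about 13% by either analysis for the true link in the table.
- Same-visit covariation of Glut and BADDs is reduced but not removed (91% to 67% above; 87% to 45% under the second set of assumptions). The result remains an association and should be described as one.
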